6.5.1 Schedule

Procedure	B	1	2	Final	LL. S.
	1	7 ± 2	14 ± 2	29 + 3	43 ± 3
Eligibility criteria	X				
Informed consent signature	X				
Pregnancy test (if applicable)	X			X	
General and ophthalmological clinical history	X				
Comprehensive ophthalmologic exploration	X	X	X	X	
Assignment of subject code	X				
Assignment to treatment group	X				
Delivery of medication and start of instillation	X				
Biomicroscopy	X	X	X	X	
Visual ability	X	X	X	X	
History of symptomatology	X	X	X	X	
OCT	X ²			X	
Tonometry	X	X	X	X	
Evaluation of concomitant medications	X	X	X	X	
Delivery of the subject's diary	X		X		

Procedure	B	1	2	Final	LL. S.
	1	7 ± 2	14 ± 2	29 + 3	43 ± 3
Evaluation of adverse events	X	X	X	X	X
Continuity evaluation		X	X	X	
Evaluation of adherence ¹		X	X	X	
Indication to change to dose reduction scheme			X		
Return of the medication				X	

¹ They are evaluated through the review of the subject's diary; the diary of the subject is reviewed in the three visits, but it is only collected in the second and final.

²The OCT can be done in a window period of 48 hours for this visit.

6.5.2 Procedures to be performed per visit

Below are the procedures that will be carried out in each visit, as well as a brief description of these.

6.5.2.1 Basal visit

- **Eligibility criteria:** refers to the review by the IP, where it states that the subject can be included in the study by meeting the inclusion criteria and not meeting the exclusion criteria. See 6.2 Eligibility criteria.
- **Informed consent signature:** refers to the signing of the written informed consent document. See 10.3 Consent
- **Pregnancy test:** refers to the performance of a rapid pregnancy test in all women of childbearing age who wish to enter the study. By fertile age we understand women who have not had their menopause, defined as 12 months since the last menstrual period in women over 40 years of age; or those who underwent bilateral hysterectomy or oophorectomy. Women of childbearing age with contraceptive methods including bilateral tubal obstruction should be tested for pregnancy. This test will be performed by the IP or the designated team person according to the instructions of the device delivered by the sponsor.
- **General and ophthalmological clinical history:** refers to the technical, clinical and legal document in which the patient's health conditions, medical acts and other procedures performed on the patient are recorded chronologically. It includes the anamnesis and comprehensive ophthalmological exploration that allows to discern the patient's eligibility. If the patient is taken from the established consultation of the study center, he / she will be able to use the existing clinical history, only having to perform an update.
- **Comprehensive ophthalmological exploration:** refers to the evaluation of the ophthalmic structures of the subject, eyelids and appendices, ocular surface, anterior segment and posterior segment; not considered within the outcome variables. This evaluation has the purpose of identifying alterations that may interfere with the course of the investigation or

identify adverse events. This scan will be recorded in the clinical file, in the CRF only what is considered an adverse event will be reported.

- Assignment of the subject's code: It refers to granting the number that will identify the patient throughout the study. This will be done according to section 6.2.4 Identification of the subject.
- Assignment to the treatment group: Refers to determining the treatment that the patient will follow during the study. It will be done according to section 7. Methods. Assignment of the intervention. This assignment will be made at the baseline visit.
- Delivery of medication: Refers to the delivery of the medication to the study patient, by the research center. It will be done according to sections 6.3.1 Managed treatments and 6.3.4.1 Delivery and reception. After each medication delivery, a training or re-training of the application of the study medication will be carried out.
- Biomicroscopy: see 6.4.3.1 Biomicroscopy
- Visual capacity: see 6.4.3.2 Visual capacity
- History of symptomatology: see 6.4.3.4 History of symptomatology
- OCT: see 6.4.3.5 Optical coherence tomography. For this visit, the OCT can be done in a window period of 48 hours.
- Tonometry: see 6.4.3.6 Tonometry

- Evaluation of concomitant medications: refers to the interrogation performed by the IP of the medications the patient uses, before, during and after the study. They must be registered in the corresponding section in the CRF, including name of active substance, posology and duration. See: 6.3.3 Treatments and concomitant interventions allowed and prohibited before and during the study.
- Evaluation of adverse events: see 6.4.3.3 Evaluation of adverse events
- Subject's daily delivery: refers to the delivery by the IP, of the subject's daily instrument, to the subject.

6.5.2.2 Visit 1.

- Comprehensive ophthalmologic exploration: see 6.5.2.1 Baseline visit.
- Biomicroscopy: see 6.4.3.1 Biomicroscopy
- Visual capacity: see 6.4.3.2 Visual capacity
- History of symptomatology: see 6.4.3.4 History of symptomatology
- Tonometry: see 6.4.3.6 Tonometry
- Evaluation of concomitant medications: see 6.5.2.1 Baseline visit.
- Evaluation of adverse events: see 6.4.3.3 Evaluation of adverse events
- Continuity assessment: refers to the determination by the IP and desire of the subject to continue with their participation in the study.
- Adherence evaluation: refers to the review of the subject's diary to evaluate the drug application registry.

6.5.2.3 Visit 2.

- Comprehensive ophthalmologic exploration: see 6.5.2.1 Baseline visit.
- Biomicroscopy: see 6.4.3.1 Biomicroscopy
- Visual capacity: see 6.4.3.2 Visual capacity
- History of symptomatology: see 6.4.3.4 History of symptomatology
- Tonometry: see 6.4.3.6 Tonometry
- Evaluation of concomitant medications: see 6.5.2.1 Baseline visit.
- Evaluation of adverse events: see 6.4.3.3 Evaluation of adverse events

- Continuity assessment: see 6.5.2.2 Visit 1
- Adherence evaluation: see 6.5.2.2 Visit 1
- Delivery of the subject's diary: see 6.5.2.1 Baseline visit, this visit is made upon delivery of the diary of the subject delivered at the baseline visit.
- Indication to change to dose reduction scheme: It refers to the indication of the IP to initiate the dose reduction scheme on day 15 of the study, and to last the remaining 14 days of the intervention. The IP will determine, according to the patient's clinical condition, the scheme to follow. It will record in the clinical note and in the CRF, the outline and total number of applications indicated. Example: 1 drop 3 times a day for 5 days; followed by 1 drop 2 times a day for 5 days; finish with 1 drop a day for 4 days; and suspend (Total number of applications indicated: 29). In case visit 2 is made on day 15 that same day, the scheme must be readjusted; if the visit is made on day 16 the scheme will be adjusted from that day and for the remaining 12 days.

6.5.2.4 Final Visit.

- Pregnancy test: see 6.5.2.1 Baseline visit.
- Ophthalmological examination: see 6.5.2.1 Baseline visit.
- Biomicroscopy: see 6.4.3.1 Biomicroscopy
- Visual capacity: see 6.4.3.2 Visual capacity
- History of symptomatology: see 6.4.3.4 History of symptomatology
- OCT: see 6.4.3.5 Optical coherence tomography
- Tonometry: see 6.4.3.6 Tonometry
- Evaluation of concomitant medications: see 6.5.2.1 Baseline visit.
- Evaluation of adverse events: see 6.4.3.3 Evaluation of adverse events
- Continuity assessment: see 6.5.2.2 Visit 1
- Adherence evaluation: see 6.5.2.2 Visit 1
- Return of the medication: refers to the delivery, by the subject, of the excess medication to the research center.

6.5.2.5 Security call:

- Evaluation of adverse events: see 6.4.3.3 Evaluation of adverse events.

6.5.3 Diagram of the study

[figure not shown]

Figure 4. Diagram of the study

6.6 Sample size.

The sample size calculated for the present study is 178 subjects.

Divided into two intervention groups, each group will be comprised of 89 subjects. Each subject will provide an eye for efficacy analysis.

6.6.1 Calculation of the sample size.

The sample size was calculated using the formula for two proportions variables as well as the data was entered into the online calculator, software developed in: www.powerandsamplesize.com based on Chow S et al. [72]

With a statistical confidence of 95% corresponding to the type I error, equal to 1.96, with a power of 80%, corresponding to the type II error, equal to 0.84. A 78.9% efficiency ratio was considered in the reduction of the degree of cells in the anterior chamber after the application of 4 weeks of difluprednate 0.05% in 79 subjects submitted to phacoemulsification compared to an efficiency ratio of 77.5% with the use of 1% prednisolone. [53]

According to the previous calculation, the result is 74 eyes per group. The total when considering 2 intervention groups is 148 eyes, which was increased by 20% (30 eyes) for the probable losses. The total sample size required is 178 eyes. **Total n = 178 eyes.**

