5.5.4 Hypothesis

H0: The use of the ophthalmic emulsion PRO-145 is not effective when decreasing the inflammatory response evaluated by means of cellularity in the anterior chamber, after phacoemulsification.

Ha: The use of the ophthalmic emulsion PRO-145 is effective in decreasing the inflammatory response evaluated by means of cellularity in the anterior chamber, after phacoemulsification.

5.6 Design and plan of the study.

Phase III clinical trial, parallel, controlled, randomized, double blind. Participants will be postsurgical phacoemulsification patients, who will be randomly assigned to 2 intervention groups with steroidal anti-inflammatory drugs. One group will receive the PRO-145 test formulation and the other group will be exposed to prednisolone acetate 1%.

[figure not shown]

Figure 2. Study design.

5.6.1 Discussion of the study design.

In clinical research it is common to propose trials with the objective of evaluating the efficacy of a product under investigation against a reference medicine or active control, in order to compare the new product under investigation from a clinical or statistical point of view to a drug commercially available

The clinical trial is the ideal model to evaluate the effectiveness of two interventions, it allows obtaining the highest quality evidence among different types of research. The characteristics of randomization and double blind, allow to avoid biases (selection, evaluation, etc.) that can not be avoided with other models. Being controlled and parallel groups allows distinguishing the effects of interventions in isolation.

The proposed clinical trial aims to evaluate the efficacy, safety and tolerability profile of a formulation of DFBA 0.05% and compare it against the safety, tolerability and efficacy profile of commercially available steroid administration, and widely used for its efficacy profile and known security.

6. Material and methods. Participants, interventions and variables.

6.1 Study Center.

The present study will be performed in ophthalmology offices duly equipped and registered for their proper functioning. According to the needs of the sponsor, these may be private or public, be attached to a hospital or clinic or be independent.

This is a multicentre study that is intended to be carried out in Guadalajara, Mexico City and Monterrey.

6.1.1 Organization of the center.

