8.3 Statistical methodology

8.3.1 Analysis of primary and secondary outcome variables

The statistical analysis will be carried out by personnel of Sophia Laboratories. The statistical program SPSS version 19 will be used.

The designated personnel will be blinded to the intervention groups. The coding will be done using consecutive numbers for each intervention group.

The data will be collected and sorted in an excel sheet. Later they will be exported to the platform of the SPSS program. The variables will be categorized according to their nature.

The results of the continuous quantitative variables will be presented in measures of central tendency: mean, standard deviation and ranges. See **Table 5 Variable measurement method**. The total size of the samples will consider an eye as a case for the evaluation of the efficacy.

The normal distribution of results will be obtained through the Kolmogorov-Smirnov and Shapiro-Wilks test, as applicable.

The statistical analysis of the continuous quantitative variables to find significant differences (p) will be the following:

. Inter-group analysis: t test for paired samples.

. Intra-group analysis: Mc Nemar test. Cellularity assessments in the anterior chamber will be considered for the analysis before the application of the intervention and in the final visit. The level of difference to consider significance will be of an alpha of 0.05 or less.

The result of nominal and ordinal qualitative variables will be presented in frequencies, proportions and percentages. See **Table 5 Method for measuring variables**

The statistical analysis to identify significant differences of the qualitative variables will be done by creating 2x2 contingency tables and will be done as follows:

- Difference between groups: χ^2 test (Chi-square) of Pearson or Fisher's exact in expected values less than 5.
- Intra-group analysis: Mc Nemar test.

The level of difference to consider significance will be an alpha of 0.05 or less.

For the reporting of adverse events all eyes of those participants who were randomly assigned to an intervention group will be considered. The results will be expressed in number of cases.

The final report of the results will be shown in tables or graphs, as appropriate.

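### The printed rates (78.9% vs 77.5%) need about 13,650 eyes per group, not 74; with 74 per group, power for that difference is about 5%, not 80%

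*Combined protocol and SAP*

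**What the plan says.** Section 6.6.1 names a two-proportion formula and an online calculator. It sets the type I error at z = 1.96, "with a power of 80%, corresponding to the type II error, equal to 0.84", and takes a rate of 78.9% for difluprednate 0.05% "compared to an efficiency ratio of 77.5% with the use of 1% prednisolone". It concludes: "According to the previous calculation, the result is 74 eyes per group". Two groups make 148 eyes, and a 20% allowance for losses (30 eyes) brings the total to 178, or 89 per group. The section gives no margin, no other target difference, and no indication whether the formula is for a difference, non-inferiority or equivalence.

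The alternative hypothesis in 5.5.4 is "The use of the ophthalmic emulsion PRO-145 is effective in decreasing the inflammatory response", with no margin. Section 5.6.1 says the trial will evaluate the test product and "compare it against the safety, tolerability and efficacy profile of commercially available steroid administration".

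On analysis, 8.3.1 says: "The statistical analysis to identify significant differences of the qualitative variables will be done by creating 2x2 contingency tables". Between groups the test is Pearson chi-square, or Fisher's exact test when expected counts fall below 5; within groups it is McNemar. It adds: "The level of difference to consider significance will be an alpha of 0.05 or less".

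**The concern.** All the inputs of a standard two-proportion calculation are printed, and they describe a difference of 1.4 percentage points. A difference that small cannot be detected with 74 eyes per group, so either an input or the result is wrong.

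Section 6.6.1 is the only justification for enrolling 178 people, and its readers will take the 80% at face value. Suppose the group comparison is a two-sided 5% chi-square on a yes/no version of cell grade. The result would then be non-significant about 95% of the time if the printed rates are true. This consequence is conditional, because 8.3.1 does not define a yes/no version of cell grade. Sections 8.3.1 to 8.3.3 plan no confidence interval and do not say how a non-significant result would be read, so it could be taken as evidence that the two steroids perform alike.

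**Working it through.** **Inputs (6.6.1).** p1 = 0.789, p2 = 0.775, difference 0.014; z = 1.96 (two-sided 5%) and 0.84 (80% power). Allocation is 1:1 (7.1).

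**1. Trying to reproduce 74**

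Sum of variances: 0.789 × 0.211 + 0.775 × 0.225 = 0.16648 + 0.17438 = 0.34085.

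Unpooled formula with the printed z values:

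n = (1.96 + 0.84)² × 0.34085 / 0.014² = 7.84 × 0.34085 / 0.000196 ≈ 13,634 per group.

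| Variant | n per group (before rounding up) |
|---|---|
| Unpooled, printed z | 13,634 |
| Pooled, printed z | 13,637 |
| Unpooled, exact z | 13,650 |
| Pooled, exact z | 13,652 |

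13,652 / 74 = 184. Relaxing the test to one-sided 5% still needs 10,752 (unpooled). No choice of pooling, rounding or sidedness comes near 74. The later step is consistent with its own rule: 148 × 1.2 = 177.6, rounded to 178.

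**2. Power at the planned size for 78.9% vs 77.5%**

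Expected non-responders per group are about 74 × 0.218 = 16.1. That is above 5, so 8.3.1 leads to Pearson chi-square.

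| Eyes per group | Normal approximation, both tails | Exact chi-square |
|---|---|---|
| 74 | 5.5% | 5.4% |
| 89 | 5.6% | 5.4% |

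**3. What 74 per group can detect**

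By the pooled formula with exact z, these pairs need 74 eyes per group for 80% power:

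- 78.9% vs 57.6%: n = 73.8; exact chi-square power 80.6%.
- 77.5% vs 93.6%: n = 73.7; exact chi-square power 82.4%.

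The detectable differences are therefore about 21 and 16 points, against the printed 1.4.

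**4. Precision**

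At 74 per group the standard error is √(0.34085 / 74) = 0.0679, and the 95% half-width is 1.96 × 0.0679 = 0.133, or 13.3 points. At 89 per group it is 1.96 × 0.0619 = 0.121, or 12.1 points.

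**5. What could have produced 74**

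None of these appears in the documents; each was found by working back from 74.

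- *Misprinted comparator rate.* 78.9% vs 57.5% gives 73.1, rounded up to 74 (pooled), or 70.4, rounded up to 71 (unpooled).
- *Non-inferiority margin.* One-sided 2.5%: (1.960 + 0.8416) × 0.0679 − 0.014 = 0.176. One-sided 5%: (1.645 + 0.8416) × 0.0679 − 0.014 = 0.155. Both assume the 1.4-point advantage is real.
- *Equivalence margin.* With 1.2816 as the power term and each one-sided test at 5%: (1.645 + 1.2816) × 0.0679 + 0.014 = 0.213. At 2.5%: (1.960 + 1.2816) × 0.0679 + 0.014 = 0.234.

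**The case against.** The strongest counter-argument is that the stated hypothesis is not about a group difference. Section 5.5.4 asks only whether PRO-145 works, 5.5.2 assesses each drug separately, and 8.3.1 includes a within-group McNemar test of cellularity before treatment and at the final visit. For that test 74 eyes is ample. If cells cleared in 20% of eyes (an assumption) and never reappeared, exact McNemar power would exceed 99%. This limits the consequence: not every planned analysis lacks power. It does not rescue 6.6.1, which uses a two-group formula with two group rates, so its 80% can only refer to the group comparison. Section 8.3.1 plans such a comparison, and 5.6.1 says this trial will make one. The other 5.6.1 phrase, "compare the new product under investigation from a clinical or statistical point of view to a drug commercially available", comes from a general remark about clinical research and carries less weight.

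A second argument is that 74 came from a non-inferiority or equivalence option in the calculator, or that a rate was misprinted. Either is possible. But a margin would be the most important design input, and it is absent from 6.6.1, the hypotheses and the analysis section. A misprint would still leave the printed calculation wrong.

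A third argument is that keeping 178 subjects cannot be endorsed while the cause is unknown. At one-sided 2.5% and the printed rates, non-inferiority needs 206 per group for a 10-point margin and 100 for 15 points, both above 89. That would matter if the sponsor now chose a new margin. The corrections below only document what 74 per group was meant to deliver, or does deliver. It is also fair to say that 74 evaluable eyes are not assured: 6.3.2 removes subjects below its adherence thresholds from the efficacy analysis, and 8.3.3 removes those without baseline or final measurements.

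**Conclusion.** The concern holds. The printed inputs require about 13,650 eyes per group, and 74 per group gives about 5% power for the printed difference. The arithmetic failure rests only on figures in 6.6.1 and does not depend on the variant of the formula. The power figures assume a two-sided 5% test on a yes/no outcome with the printed rates as true values.

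The documents do not show which element is wrong. What follows for the trial's conclusions is conditional on a yes/no cell endpoint being compared between groups. Two side observations bear on the correction: 6.6.1 describes its rates as reduction of cells while 5.5.2 speaks of elimination, and the reference cited for the rates is a paediatric study.

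**What to change.** Retrieve the original calculation and amend 6.6.1 according to what it shows. In every case, name the yes/no definition of cell grade to which the rates refer.

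- **(a) A rate was misprinted.** Print the correct rate and confirm that it yields 74.
- **(b) A margin was pre-specified** (non-inferiority or equivalence). Print the margin, its justification, its sidedness and the power at 74 per group, and bring 5.5.4 and 8.3.1 into line with it.
- **(c) Neither applies.** Withdraw the 80% claim for 78.9% vs 77.5% and state in 6.6.1:

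> With 74 evaluable eyes per group and a two-sided 5% test of difference (pooled formula), power is 80% for 78.9% versus about 57.6%, or for 77.5% versus about 93.6%; it is about 5% for 78.9% versus 77.5%.

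In case (c), also add to 8.3.1:

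> The difference between groups will be reported with a 95% confidence interval (about 13 points either side at 74 per group). A non-significant result will not be interpreted as similar efficacy.

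The case (c) figures describe what 178 subjects can detect; they are not a clinical justification for that number.

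**Cost.** No extra patients. Case (a) changes 6.6.1, and 8.3.1 if the endpoint definition is placed there. Case (b) changes 6.6.1, 5.5.4 and 8.3.1. Case (c) changes 6.6.1 and 8.3.1, with a less favourable power statement and one added interval. Each goes through the amendment procedure in 10.2.

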6.7 Recruitment

The subjects will be recruited from the outpatient IP consultation and who have met the criteria for cataract surgery by phacoemulsification. The IP may include subjects who are not operated on their own, as long as the surgeon responsible for the surgery hands over the postoperative management to the IP and its equipment.

7. Methods Assignment of the intervention

7.1 Generation of the allocation sequence.

2 strata corresponding to the intervention groups will be used, which will be balanced for each research center. The allocation will be 1: 1. The generation will be done through an electronic system validated by an external provider, previously evaluated and authorized by Sophia Laboratories S.A. of C.V. The information corresponding to this provider will be found in the master folder of the study.

7.2 Blinding mechanism

Blinding will be performed by the personnel indicated by the Clinical Operations Management of Sophia Laboratories, S.A. of C.V. The vials of both interventions will be re-labeled and the secondary packaging will be masked.

7.3 Implementation

The sequence will be generated by means of an electronic randomisation system. Said system will be hired by Sophia Laboratories, S.A. of C.V. to a third party. The information corresponding to this third party will be found in the master folder of the study.

